2.0 Study Objectives and Design

2.1 Study Objectives

Primary Objective

The primary objective is to assess the efficacy, safety, and tolerability of cariprazine in comparison to placebo in subjects from Japan and Taiwan with acute exacerbation of schizophrenia.

Primary Efficacy Objective

The primary efficacy objective is to determine if cariprazine (6 mg/day) improves the Structured Clinical Interview for the Positive and Negative Syndrome Scale (SCI-PANSS) total score compared to placebo in subjects from Japan and Taiwan with acute exacerbation of schizophrenia.

The hypothesis corresponding to the primary efficacy objective is that decrease in SCI-PANSS total score with cariprazine (6 mg/day) is greater than that with placebo.

The attributes of the primary estimand corresponding to the primary efficacy objective are as follows:

- Population: The modified intent-to-treat (mITT) population, which consists of all randomized subjects who receive at least 1 dose of study drug and have both baseline and at least 1 postbaseline value of SCI-PANSS total score during the double-blind period (DBP).
- Variable: The primary efficacy endpoint, change from baseline to Week 6 of the DBP in SCI-PANSS total score.
- Accounting for intercurrent events: regardless of whether rescue medications are used, data are included in the analysis. Data after discontinuation of study drug will not be included in the primary analysis and will be assumed missing at random.
- Population-level summary: The difference in means between cariprazine 6 mg/day and placebo.

Secondary Objectives

The secondary objective is to assess the maintenance of efficacy, safety, and tolerability of cariprazine in an 18-week blinded extension period (BEP) in subjects who completed the DBP of this study.

[figure not shown]
2.2 Study Design Overview

This is a randomized, double-blind, placebo-controlled Phase 3 study consisting of a 6-week DBP to assess the safety, tolerability, PK, and efficacy of cariprazine in subjects from Japan and Taiwan with acute exacerbation of schizophrenia, followed by an 18-week BEP.

This study consists of a screening period, a 6-week DBP, an 18-week BEP, and an 8-week follow-up period. The study has a planned enrollment of approximately 250 subjects (125 subjects per arm), randomized on Day 1 (Visit 2) in a 1:1 ratio to placebo or cariprazine 6 mg/day. Subjects who complete the DBP will have the option to enter the 18-week BEP, during which subjects who received placebo during the DBP will be switched to cariprazine 1.5 mg/day and subjects who received cariprazine 6 mg/day during the DBP will receive cariprazine 3 mg/day in a blinded manner in the BEP. Study sites and subjects will remain blinded to treatment assignment for the duration of the study.

The schematic of the study is shown in Figure 1.

Figure 1. Study Schematic

Handling of data from subjects who were randomized to cariprazine 3 mg/day prior to removal of this dose arm from the DBP

The data from subjects who were randomized to cariprazine 3 mg/day prior to removal of this dose arm from the DBP will be included in analyses of the DBP.

2.3 Treatment Assignment and Blinding

All subjects will be assigned a unique identification number by the interactive response technology (IRT) at screening (Visit 1). Approximately 250 subjects (125 subjects per arm) will be randomized to either the placebo arm or the cariprazine 6 mg/day arm in a 1:1 ratio on Day 1 (Visit 2). The randomization will be stratified by study site. The IRT will assign a randomization number that will encode the subject's treatment group assignment according to the randomization schedule.

All AbbVie personnel with direct oversight of the conduct and management of the trial (with the exception of AbbVie Drug Supply Management Team) will remain blinded to each subject's treatment until database lock after DBP. The investigator, study site personnel, and the subject will remain blinded to each subject's treatment throughout the study. To maintain the blind, the cariprazine capsules and placebo capsules provided for the study will be identical in appearance. The IRT will provide access to unblinded subject treatment information in the case of a medical emergency.

2.4 Sample Size Determination

In terms of the change from baseline in the SCI-PANSS total score at Week 6, the sample size of 125 subjects per arm (N = 250) can achieve at least 90% power at overall 0.05 two-sided significant level to detect the statistically significant difference between placebo and cariprazine 6 mg/day based on these assumptions using a Mixed-Effect Model for Repeated Measurement (MMRM); treatment difference of -8.3 between 6 mg/day and placebo based on the full analysis set (FAS) 2 in Studies A002-A4 and RGH-MD-04, and common standard deviation of 20 at Week 6 taking into account dropout rates and correlation matrix based on FAS in Study A002-A4.

3.0 Endpoints

The following endpoint definitions apply to the efficacy variables described below:

3.1 Primary Endpoint

- Change in SCI-PANSS total score from baseline to DBP Week 6.

3.2 Secondary Endpoint

3.2.1 Key Secondary Endpoint for DBP

- Change in Clinical Global Impression-Severity (CGI-S) score from baseline to Week 6

3.2.2 Additional Secondary Endpoints for DBP

- Change in SCI-PANSS positive symptom score from baseline to Week 6
- Change in 16-Item Negative Symptom Assessment (NSA-16) total score to baseline to Week 6
- Change in SCI-PANSS negative symptom score from baseline to Week 6
- Change in SCI-PANSS negative factor score from baseline to Week 6

3.2.3 Efficacy Endpoints for BEP

- Change in SCI-PANSS total score from baseline and Week 6 to Week 24
- Change in CGI-S score from baseline and Week 6 to Week 24
- Change in SCI-PANSS positive score from baseline and Week 6 to Week 24
- Change in NSA-16 total score from baseline and Week 6 to Week 24
- Change in SCI-PANSS negative symptom score from baseline and Week 6 to Week 24
- Change in SCI-PANSS negative factor score from baseline and Week 6 to Week 24

3.3 Safety Endpoints

The safety endpoints are as follows:

- Adverse Events (AEs)
- Clinical laboratory tests
- Vital signs
- Electrocardiogram (ECG)
- Suicide severity rating (Columbia-Suicide Severity Rating Scale [C-SSRS])
- Extrapyramidal symptom (EPS) assessment:
 - Simpson-Angus Scale (SAS)
 - Abnormal Involuntary Movement Scale (AIMS)
 - Barnes Akathisia Rating Scale (BARS)

4.0 Analysis Populations

The following population sets will be used for the analyses.

Modified Intent-To-Treat (mITT) Population

The Modified Intent-To-Treat (mITT) population includes all randomized subjects who receive at least 1 dose of study drug and have both baseline and at least 1 postbaseline value of SCI-PANSS total score during the DBP. The mITT population will be used for all efficacy analyses for the DBP. Subjects will be included in the analysis according to the treatment group to which they were randomized (as randomized).

Safety Population

The safety population includes all randomized subjects who receive at least 1 dose of study drug. Subjects will be included in the treatment group corresponding to the double-blind treatment they actually receive in the safety population. The safety population will be used for demographic and safety analyses for the DBP. A subject's actual treatment

group will be determined by the kit type dosed most frequently during the DBP as follows:

- Placebo dose card: Placebo
- 3.0 mg dose card or 3.0 mg titration card: 3.0 mg/day (only for summaries described in Section 2.2)
- 6.0 mg dose card or 6.0 mg titration card: 6.0 mg/day

Kit types in the RN_KIT dataset will be described in the Statistical Programming Plan (SPP).

BEP Population

The BEP population will consist of all subjects who complete the 6-week DBP and take at least 1 dose of study drug during the BEP regardless of which treatment group they were randomized to during the DBP. Subjects will be grouped according to their modal (most frequent) daily dose during the BEP. The BEP population will be used for efficacy and safety analyses for the BEP.

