5.6 Follow-Up After Subject Discontinuation of Study Drug or from Study

Subjects who discontinue study treatment during the DBP or the BEP of the study will undertake the examinations and observations for the PD visit. Allowable time window for scheduled examination is within 3 days from the last administration of study drug (or within 14 days for the ophthalmologic examination). Subjects who discontinued study treatment during the DBP or the BEP will enter the safety follow-up period. For subjects who prematurely discontinue the safety follow-up period, the visit window for the PD visit is within 7 days after discontinuation.

If a subject prematurely discontinues study participation (withdrawal of informed consent), the procedures outlined for the PD visit should be completed within 3 days of the last administration of study drug. Subjects should be advised on the continued scientific importance of their data even if they discontinue treatment with study drug early. In addition, if a subject is willing, a 30-day follow-up phone call after the last dose of study drug may be completed to ensure all treatment-emergent AEs (TEAEs)/serious adverse events (SAEs) have been resolved.

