APPENDIX D. ACTIVITY SCHEDULE

The following table shows the required activities prior to and across the 8 subject visits in the 6-week DBP. Subjects who do not enter the BEP are required to enter the 8-week safety follow-up period (safety follow-up period includes 3 subject visits) after the last dose of the study drug in the 6-week DBP. Study activities for the safety follow-up period are detailed in the Study Activities Table for the Blinded Extension Period and Safety Follow-Up Period.

The individual activities are described in detail in the **Operations Manual**. Allowed modifications due to COVID-19 are detailed in the **Operations Manual**.

Study Activities Table for the 6-Week Double-Blind Period

	Informed Consent	Screening	Baseline	Wk1	Wk2	Wk3	Wk4	Wk5	Wk6/PD
Visit #	-	1	2	3	4	5	6	7	8
Visit window (days)						±3			-1/+3
Activity		up to Day -14	Day 1	Day 8	Day 15	Day 22	Day 29	Day 36	Day 43
❑ INTERVIEWS & QUESTIONNAIRES									
Subject information and informed consent	✓								
Eligibility criteria		✓	✓						
DSM-5 and MINI		✓							
Medical/surgical history		✓	✓						
Adverse event assessment		✓	✓	✓	✓	✓	✓	✓	✓
Prior/concomitant therapy		✓	✓	✓	✓	✓	✓	✓	✓
SCI-PANSS		✓	✓	✓	✓	✓	✓	✓	✓
CGI-S		✓	✓	✓	✓	✓	✓	✓	✓
NSA-16			✓		✓		✓		✓
C-SSRS		✓	✓	✓	✓	✓	✓	✓	✓
❑ LOCAL LABS & EXAMS									
SAS/AIMS/BARS			✓	✓	✓	✓	✓	✓	✓
Vital signs		✓	✓	✓	✓	✓	✓	✓	✓
Physical examination (include height*, weight) *Height at screening only		✓							
12-lead ECG		✓							✓
Ophthalmologic examinations (slit-lamp, BCVA, and intraocular pressure during screening period. Only BCVA at Wk 6/PD permitted +14 days.)		✓							✓

	Informed Consent	Screening	Baseline	Wk1	Wk2	Wk3	Wk4	Wk5	Wk6/PD
Visit #	-	1	2	3	4	5	6	7	8
Visit window (days)					±3				-1/+3
Activity		up to Day -14	Day 1	Day 8	Day 15	Day 22	Day 29	Day 36	Day 43
LABS									
Serum pregnancy test (for all female subjects of childbearing age)		✓							✓
Hematology		✓			✓		✓		✓
Clinical chemistry, urinalysis, and urine myoglobin (urine myoglobin as necessitated by symptoms/lab values)		✓			✓		✓		✓
HbA1c, prolactin, fasting insulin, TSH/T4/T3, LH, FSH		✓							✓
HIV, HBV, and HCV		✓							
Pharmacokinetic (PK) sample				✓		✓			✓
Blood or urine alcohol level		✓ (blood or urine)							✓ (blood only)
Urine drug screening		✓							✓
TREATMENT									
Randomization/drug assignment			✓						
Administration of study drug/placebo			✓	✓	✓	✓	✓	✓	✓

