9.2.1 Continuous Endpoints

For missing data of continuous efficacy endpoints for the DBP and BEP, descriptive statistics and figures is provided using the following approach:

- LOCF: Only the post-baseline total score of a parameter will be imputed. Individual item score will not be carried forward. Baseline total score will be carried forward only for the intermittent missing scores immediately after baseline. If all the post-baseline values are missing, baseline value will not be carried forward.
- OC: The OC analysis will not impute values for missing evaluations, and thus a subject who does not have an evaluation on a scheduled visit will be excluded from the OC analysis for that visit. OC will exclude values after a subject prematurely discontinues from study treatment.

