9.2.2 Categorical Endpoints

For binary efficacy endpoints where logistic regression model is performed, missing data will be handled using the LOCF approach, the OC approach and the following approaches:

- Non-Responder Imputation (NRI): the NRI method will categorize any subject who does not have evaluation during a specific visit window as a non-responder for that visit.

The LOCF and OC approaches used for categorical efficacy endpoints are defined as the same method as for continuous efficacy endpoints.

Response for each subject will be derived based on the imputed score.

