9.4.4 Additional Efficacy Endpoints and Analyses

The additional efficacy endpoints for DBP are:

- PANSS responder (subjects with SCI-PANSS total score improved by $\geq 30\%$ at Week 6 compared with Baseline)

For the PANSS responder, the number, percent and 2-sided 95% CI will be provided using the LOCF approach, the OC approach or the NRI approach, respectively. Details on the analysis, output are specified in Section 9.1 and Section 9.2.2.

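### Non-responder imputation for the PANSS responder endpoint is run on the mITT, so a dosed subject with no post-baseline SCI-PANSS leaves the denominator instead of counting as a non-responder

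*SAP*

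**What the plan says.** **Population.** SAP 4.0 admits a randomised subject to the mITT only if the subject took study drug and "have both baseline and at least 1 postbaseline value of SCI-PANSS total score during the DBP". It then states: "The mITT population will be used for all efficacy analyses for the DBP". SAP 9.1 repeats that use.

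**Imputation rule.** SAP 9.2.2 says that "the NRI method will categorize any subject who does not have evaluation during a specific visit window as a non-responder for that visit". SAP 9.4.4 applies this to the PANSS responder (at least 30% improvement in SCI-PANSS total score at Week 6), with number, percent and 95% CI given "using the LOCF approach, the OC approach or the NRI approach, respectively". It names no population wider than the mITT.

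**LOCF.** SAP 9.2.1 says: "If all the post-baseline values are missing, baseline value will not be carried forward".

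**Early stoppers.** For subjects who stop treatment, Protocol 5.6 requires the PD examinations: "Allowable time window for scheduled examination is within 3 days from the last administration of study drug". In Protocol Appendix D, SCI-PANSS is ticked at Week 1 (Day 8) and in the combined Week 6/PD column. SAP 8.0 keeps data from the day of the last dose and excludes data after discontinuation.

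**The concern.** NRI exists so that a subject who leaves without an outcome counts against the arm. That works only if the subject is in the denominator. Here the population rule acts first: a dosed subject with no post-baseline score is outside the mITT, so the imputation rule never reaches that subject. The reported NRI rate then does not follow its own definition, and within an arm the error can only be upward. With 34 subjects randomised (SAP 1.0), one person is a visible share of an arm. Efficacy reporting is now purely descriptive, so the rates and intervals are the efficacy result.

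**Working it through.** **The plan's own figure.** The plan gives no number on this point. Its one calculated figure, at least 90% power with 125 per arm, reproduces with a two-sample normal formula and no loss to dropout: 8.3/(20 × √(2/125)) = 3.28; 3.28 − 1.96 = 1.32; power 90.7%. It concerns the mean change at Week 6 and is not affected.

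**Who is lost.** Take dosed subjects with a baseline score:

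- At least one usable post-baseline score but none at Week 6: in the mITT, and NRI counts a non-responder as intended.
- Stopped before Day 8, with a PD score on the day of the last dose: in the mITT, and handled as intended.
- Stopped before Day 8, with a PD score one to three days after the last dose: unclear. SAP 4.0 does not say whether a score that SAP 8.0 excludes from analysis still qualifies a subject for the mITT, and neither document says when the double-blind period ends for someone who stops early. If the score qualifies, NRI counts a non-responder; if not, the subject disappears.
- No post-baseline SCI-PANSS at all: outside the mITT and never imputed.

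No other efficacy analysis recovers the last group. LOCF does not carry baseline forward, observed cases exclude them, and none of the efficacy analyses uses all dosed subjects.

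**Size within an arm.** Let n be the number dosed, r the responders and k the number dosed with no qualifying post-baseline score. The rate on all dosed subjects is r/n. The rate on the mITT is r/(n − k) = (r/n) × n/(n − k), which is never lower.

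The documents give neither k nor the arm sizes. I assume n from 11 to 17, because 34/3 = 11.3 (the 3 mg/day arm is now included) and 34/2 = 17. The r values are also assumed.

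| n, r | All dosed | k = 1 | k = 2 | k = 3 |
|---|---|---|---|---|
| 11, 4 | 4/11 = 36.4% | 4/10 = 40.0% | 4/9 = 44.4% | 4/8 = 50.0% |
| 17, 5 | 5/17 = 29.4% | 5/16 = 31.25% | 5/15 = 33.3% | 5/14 = 35.7% |

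For one excluded subject the rise is 40.0 − 36.4 = 3.6 points or 31.25 − 29.4 = 1.8 points. With k = 0 it is zero.

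**Difference between arms.** Assume 17 per arm with 6 and 4 responders. On all dosed subjects the difference is 6/17 − 4/17 = 11.8 points. Losing two cariprazine subjects gives 6/15 − 4/17 = 16.5. Losing two placebo subjects gives 6/17 − 4/15 = 8.6. The sign of the distortion depends on which arm loses more.

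**The case against.** The strongest reply is that the plan already catches most early stoppers. A reader might infer that everyone who stops before the first scheduled post-baseline visit is excluded. The documents do not support that. PD examinations include SCI-PANSS, Protocol 5.6 asks for them after consent withdrawal too, and the mITT definition does not require the qualifying score to be on treatment. Subjects also stay in hospital at least until Week 2 (Protocol 4.1), so the exposed days before Day 8 fall within the inpatient stay. This stands, and it makes k probably small.

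Consequence is also limited. NRI serves one additional endpoint that is absent from Protocol 3.3, LOCF and observed-case versions sit beside it, and no tests are run (SAP 9.1 and 12.0). Sampling error is far larger: for 4/11, 1.96 × √(0.364 × 0.636/11) gives a rough half-width of 28 points, against a shift of 3.6. The disposition table in SAP 5.0 lets a reader approximate the corrected rate. All of this stands. None of it makes the denominator match the stated rule.

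A second inference is that the primary result is biased because the estimand population is itself the mITT (SAP 2.1: "Population: The modified intent-to-treat (mITT) population, which consists of all randomized subjects who receive at least 1 dose of study drug", with the post-baseline requirement following). Defining a target population by an assessment made after randomisation is indeed poor form. But the final SAP reports only LOCF and observed-case summaries for the primary and key secondary endpoints. A subject with no post-baseline value contributes no change score to either, so rewording the population alters no such result. A population defined by having taken study drug would also depend on something after randomisation.

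**Conclusion.** The point holds in a narrow form. As written, the NRI responder rate omits dosed subjects with no post-baseline SCI-PANSS, contrary to the rule in SAP 9.2.2, and SAP 4.0 leaves open whether a PD score taken after the last dose keeps a subject in. The within-arm inflation is exactly n/(n − k): about 2 to 4 points for one excluded subject under the assumed arms of 11 to 17 and rates of about 30 to 36%, and nothing if k = 0. These sizes rest on assumed arm sizes and responder counts.

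A reader might go further and infer that NRI is defeated for dropouts in general, or that the comparison is tilted towards cariprazine. Neither follows. NRI works for every mITT subject who lacks a Week 6 evaluation, and the documents do not show which arm, if any, loses more subjects. No test decision or type I error rate is involved. The change is worth making because it is nearly free and can only remove upward bias within an arm.

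**What to change.** In SAP 9.4.4, specify that the NRI responder summary uses all randomised subjects who took study drug and have a baseline SCI-PANSS, grouped as randomised. Baseline SCI-PANSS is needed for eligibility (Protocol 5.1, criterion 11), so that condition should remove almost nobody. Keep the mITT for LOCF and observed cases. Report the number of dosed subjects excluded from the mITT by arm. This also removes, for NRI, the ambiguity over late PD scores.

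Cost: a sentence in 9.4.4, a matching exception in SAP 4.0, and a line in SAP 13.1, because Protocol 7.2 assigns the mITT to all double-blind efficacy analyses. The endpoint is not in the protocol's list, so no endpoint changes. The downside is that responder rates may be slightly lower and that the NRI denominator may differ from the LOCF one, which needs a footnote. Rewording the estimand population in SAP 2.1 and Tables 1 and 2 is optional and changes no primary or key secondary result.

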5.0 Subject Disposition

A summary of subject accountability during the DBP will be provided where the number of subjects in each of the following categories will be tabulated for each treatment group and overall for all randomized subjects:

- Subjects randomized in the study;
- Subjects who took at least one dose of study treatment;
- Subjects who took at least one dose of study treatment (mITT population and safety population);
- Subjects who completed study treatment (mITT population and safety population);
- Subjects who prematurely discontinued study treatment (mITT population and safety population);

A summary of subject accountability during the BEP will be provided where the number of subjects in each of the following categories will be tabulated for each modal daily dose in the BEP population:

- Subjects who took at least one dose of study treatment;
- Subjects who completed study treatment;
- Subjects who prematurely discontinued study treatment;

The number and percentage of subjects who discontinued study drug during the DBP will be summarized by reason for each treatment group and overall for the all randomized subjects.

The number and percentage of subjects who discontinued study during the DBP will be summarized by reason for each treatment group and overall for the all randomized subjects.

The number and percentage of subjects who completed the DBP but did not enter the BEP will be summarized by reason for each treatment group and overall for all randomized subjects. In addition, the number and percentage of subjects in each treatment group according to modal daily dose for the BEP will be summarized by treatment group and overall according to randomization for the DBP for all randomized subjects.

The number and percentage of subjects who discontinued study drug during the BEP will be summarized by reason for each modal daily dose and overall for the BEP population.

The number and percentage of subjects who discontinued study during the BEP will be summarized by reason for each modal daily dose and overall for the BEP population.

